The main aim of this proposal is aligned with the studies above. We propose to improve the FFR-CT accuracy using the new opportunities offered by 3D printing. Namely we will develop very accurate coronary models using 3D printing and use these phantoms to optimize the FFR-CT approach. Next we propose to use the optimized approach to perform a small clinical study at Gates Vascular Institute where we will correlate the FFR-CT results with angio FFR and patient follow-up.

Summary of Proposed Research

Coronary Computed Tomography Angiography (CCTA) contrast opacification gradients and FFR-CT estimation can aid in the severity estimation of significant atherosclerotic lesions. Following this trend, we recently developed a collaboration between Brigham and Women's Hospital (BWH) and Gates Vascular Institute (GVI). We 3D-printed patient specific coronary phantoms at (GVI) and scanned them with a Toshiba Aquilion scanner to test several aspects of the contrast opacification gradients using a method established at BWH. Our initial results showed strong correlation between the flow in the phantom and opacification gradients. We believe that this approach could be further developed to test and validate FFR-CT algorithms. Currently, FFR-CT algorithms can only be optimized using theoretical models and can only be validated in large multi-center clinical trials. This phantom approach would allow optimization of FFR-CT algorithms with a measured validation technique without the need for large clinical trials. Thus we believe that this study will result in a FFR-CT algorithm/method with a better predictability for arterial lesion severity than those existing on the market today. Our approach is to use the infrastructure at GVI to perform a detailed validation of the FFR-CT method using 3D printed patient specific phantoms. Each patient will have a 3D phantom printed, containing the culprit lesion and used in a benchtop flow analysis. Flow measurements will be compared with: CT-FFR for both patients and phantoms, angio lab FFR measurements and 30 days follow-up. This pilot clinical study will include ~50 patients over a year and half at GVI. We are confident that this approach performed via 3D-phantom testing will prove the validity of FFR-CT based measurements as well as develop a new standard for validating FFR-CT algorithms

Objectives

- To build 50 3D printed patient specific phantoms for benchtop testing to determine pressure gradient along diseased vasculature

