- To perform a detailed validation of the FFR-CT method using 3D printed patient specific phantoms
- Optimization of FFR-CT algorithms with a better predictability for arterial lesion severity without the need for large clinical trials

Hypotheses

Flow simulations in 3D printed patient specific phantoms will correlate with CT derived fractional flow reserve calculations. To demonstrate the concept feasibility, we propose to use 3D printed cardiac models for software validation using clinical evaluation as a gold standard. The clinical cases will be used both as ground truth to demonstrate the accuracy of the phantom validation as well as a pilot single-center clinical evaluation to demonstrate similar results to previously published clinical trials for algorithms similar to those being tested.

Study Design/ Procedures

Patients will be consented after CCTA. First requirement is that the patient has at least one lesion with >50% stenosis or 30-50% if clinically driven. Second requirement is that the patient undergoes a cath lab intervention. If one of the above requirements is not satisfied the patient will be removed from the study. Viable candidates based on inclusion/exclusion criteria will undergo clinically indicated first generation 320-detector row CCTA (Aquilion ONE, Canon Medical Systems, Tustin, CA) with 0.5 mm slice thickness, automated tube current modulation, 100 kVp, and a reconstructed voxel size of 0.625x0.625x0.5 mm. Next, the patient will undergo catheter lab procedure as clinically warranted. The invasive FFR will be done on the culprit lesion(s) for clinical purposes. Invasive FFR (I-FFR) will be recorded via pressure wire at a distance of two lesion lengths past the distal end of the lesion. A FFR cutoff value of less than or equal to 0.8 was used to determine hemodynamic significance.

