R denotes the ratio of the number of patients without the condition to patients with the condition in the study sample. Using results from previous reports on CT-FFR [25], we set R=1.2. For an AUROC=0.8 the parameter may be set to 1.19 [24]. Thus the number of samples with FFR<=0.80 are approximatively 23 and the total number of subject given by N_total=n(1+R) is approximatively 52.

Study Flow Chart

Statistical Analysis

The absolute error as a percentage with 95% confidence intervals and Pearson correlation values will be calculated to assess the results obtained from the benchtop flow testing and the CT-FFR software and how they compared to the I-FFR reference standard. A ROC curve will also be generated to determine the area under the curve (AUC) for B-FFR and CT-FFR when compared to I-FFR. Statistical analysis for the development of the ROC curves and correlation analysis will be completed within NCSS Statistical Software (NCSS, v.12, LLC, Kaysville, Utah).

References

1. Brown, B.G., et al., Quantitative coronary arteriography: estimation of dimensions, hemodynamic resistance, and atheroma mass of coronary artery lesions using the arteriogram and digital computation. Circulation, 1977. 55(2): p. 329-337.

2. Qureshi, A.I., et al., Prevention and treatment of thromboembolic and ischemic complications associated with endovascular procedures: Part I— Pathophysiological and pharmacological features. Neurosurgery, 2000. 46(6): p. 1344-1359.

3. [name], K.K., et al., Diagnostic accuracy of 3D deep-learning-based fully automated estimation of patient-level minimum fractional flow reserve from coronary computed tomography angiography. European Heart Journal - Cardiovascular Imaging, 2019.

4. Tang, C.X., et al., Diagnostic performance of fractional flow reserve derived from coronary CT angiography for detection of lesion-specific ischemia: A multi-center study and meta-analysis. Eur J Radiol, 2019. 116: p. 90-97.

5. Morris, P.D., et al., Virtual fractional flow reserve from coronary angiography: modeling the significance of coronary lesions: results from the VIRTU-1 (VIRTUal Fractional Flow Reserve From Coronary Angiography) study. JACC Cardiovasc Interv, 2013. 6(2): p. 149-57.

6. Morris, P.D., et al., Computational fluid dynamics modelling in cardiovascular medicine. Heart, 2016. 102(1): p. 18-28.

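### No signed difference is planned, so the planned measures cannot show whether B-FFR or CT-FFR reads high or low, and the two are never compared with each other

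*Combined protocol and SAP*

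**What the plan says.** The Statistical Analysis section is one short paragraph. It plans three measures, all with I-FFR as the reference:

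- Error and correlation: "The absolute error as a percentage with 95% confidence intervals and Pearson correlation values will be calculated".
- Discrimination: "A ROC curve will also be generated to determine the area under the curve (AUC) for B-FFR and CT-FFR when compared to I-FFR".

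No formula or sign convention is given for absolute error. No mean difference, bias or limits of agreement appears anywhere in the document.

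Other sections ask for more:

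- Hypotheses: "Flow simulations in 3D printed patient specific phantoms will correlate with CT derived fractional flow reserve calculations".
- Summary of Proposed Research: "Flow measurements will be compared with: CT-FFR for both patients and phantoms, angio lab FFR measurements and 30 days follow-up". The same section expects the work to prove FFR-CT valid and to set a standard for validating such algorithms.
- Objectives: "Optimization of FFR-CT algorithms with a better predictability for arterial lesion severity without the need for large clinical trials".
- Study Design/ Procedures: "A FFR cutoff value of less than or equal to 0.8 was used to determine hemodynamic significance". No sensitivity or specificity of B-FFR or CT-FFR at that cutoff is promised.

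**The concern.** Validating or tuning a measurement method requires knowing how far it sits from the reference, and on which side. Of the three planned measures only absolute error reflects distance. Read as unsigned, it drops the sign and merges a systematic offset with random scatter. A method that overstates FFR, and so misses significant lesions, could then look the same as one that understates FFR and flags too many.

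An offset is plausible, though the documents give no evidence of one. The Figure 2 legend says bench aortic pressure and distal flow are set with adjustable clamps, and CT-FFR is a computed value.

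The second gap is between hypothesis and analysis. The hypothesis sets phantom flow against CT-FFR, but the analysis names only I-FFR as comparator. Two methods offset in opposite directions can score alike against I-FFR and still disagree with each other.

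**Working it through.** **Inputs from the documents.** Cutoff 0.80. Ratio without to with the condition R = 1.2, so 1/2.2 = 45% at or below 0.80. AUROC 0.80 ("For an AUROC=0.8 the parameter may be set to 1.19"; √2 × 0.8416 = 1.190 agrees). N about 52, with 23 at or below 0.80.

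The stated N follows if the variance term uses exp(-a²/2) and (a² + 8)/R. Then V = 0.1118, n = 1.75² × 0.1118 / 0.12² = 23.8, and N = 23.8 × 2.2 = 52.3. The variance formula as it appears in the text gives about 260. That is a separate matter, and N = 52 is taken as stated here.

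**Assumptions, not in the documents.** I-FFR has mean 0.811 and SD 0.10 and is capped at 1. The method reading is T = I + e + b, where e is symmetric normal error with SD 0.12 (which gives AUROC 0.80) and b is a constant offset. T is uncapped in the main case.

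**Step 1: effect of b, by algebra.**

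- Pearson r: adding b changes neither the covariance with I nor the SD of T, so r is unchanged.
- AUC is the probability that a diseased reading is lower than a non-diseased one; b cancels.
- Mean unsigned error is E(|e + b| / I). With e symmetric, +b and -b give the same value.
- Sensitivity is P(I + e ≤ 0.80 - b, given I ≤ 0.80), which moves directly with b.

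**Step 2: size, by simulation (1,000,000 draws).**

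| Offset | r | AUC | Absolute error | Sensitivity | Specificity |
|---|---|---|---|---|---|
| 0 | 0.63 | 0.80 | 12.0% | 71% | 73% |
| +0.05 | 0.63 | 0.80 | 13.0% | 57% | 84% |
| -0.05 | 0.63 | 0.80 | 13.0% | 83% | 59% |

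Mixing of offset and scatter: an offset of 0.093 with error SD 0.06 also gives 12.0% absolute error, the same as no offset with error SD 0.12. Here r and AUC would separate the two cases, so the example concerns absolute error alone.

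**Step 3: what a signed difference would show at N = 52.** The 95% CI half-width is 2.008 × 0.12 / √52 = 0.033. For an offset of 0.05 the noncentrality is 0.05 / (0.12/√52) = 3.0, and the CI excludes zero on the correct side in about 84% of studies, for either sign.

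**Step 4: B-FFR against CT-FFR.** Take B-FFR at +0.05, CT-FFR at -0.05 and independent errors. The mean gap is 0.10, its SD is 0.12 × √2 = 0.170, and the half-width is 2.008 × 0.170 / √52 = 0.047. The direction shows in 99% of studies. Against I-FFR the two methods have the same r, AUC and expected absolute error.

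**Step 5: range.** Error SD is re-solved for AUROC about 0.80.

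- I-FFR SD 0.08 (error SD 0.097): sensitivity/specificity about 53/86% at +0.05 and 85/56% at -0.05; direction detected in about 95%.
- I-FFR SD 0.12 (error SD 0.143): about 60/82% and 81/61%; direction detected in about 70%.
- T capped at 1 (I-FFR SD 0.10, error SD 0.12): sensitivity/specificity unchanged; absolute error 11.4% at +0.05 and 12.6% at -0.05; r 0.618 and 0.630; direction detected in about 65% and 92%.

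**The case against.** **Nothing planned is wrong.** Pearson r answers a hypothesis worded as correlation, AUC is what the study is sized on, and an error measure with a confidence interval is present. This is a pilot feasibility study, and the missing quantities can be computed later from the same paired data. All of this stands and limits the severity.

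**Absolute error is undefined.** It might mean a difference in FFR points rather than a relative one, with the sign kept. In that case the complaint about direction falls away. This stands as a condition on the conclusion, and it is itself a reason to define the term.

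**The 0.80 point lies on the planned ROC curve, and no rival threshold is named.** This also stands. That part is only a missing commitment to report.

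**The illustration is idealised.** The 0.05 offset is hypothetical. With no cap, about 18% of readings exceed 1 at +0.05. Capping makes the two directions slightly unequal and lowers detection of a positive offset to 65%. Those small inequalities would still not tell a reader which way a method errs, and the contrast in sensitivity and specificity is unaffected.

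**The missing B-FFR versus CT-FFR comparison is a distinct issue.** It is a mismatch between hypothesis and analysis rather than a question of sign. That is fair, but the same added analysis settles both.

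**Conclusion.** The concern holds. No signed difference, limits of agreement or B-FFR versus CT-FFR comparison is planned. If absolute error is unsigned, the three planned measures cannot separate a method that reads high from one that reads low. Under the stated assumptions, offsets of +0.05 and -0.05 leave the planned results alike while sensitivity at 0.80 differs by 83 - 57 = 26 points and specificity by 84 - 59 = 25 points. These figures show what could go unseen; they do not estimate a bias in this study. The planned analyses remain valid for what they measure, so this is a worthwhile improvement rather than a flaw that undermines the study. The signed differences and the missing pair are the substance. The definition of absolute error and the 0.80 operating point are matters of reporting detail.

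**What to change.** In the Statistical Analysis section:

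1. Define absolute percent error as |method - I-FFR| / I-FFR, unsigned.
2. Add the mean signed difference with 95% CI and 95% limits of agreement (Bland-Altman) for B-FFR minus I-FFR, CT-FFR minus I-FFR, and B-FFR minus CT-FFR. Report Pearson r for the last pair too, because the hypothesis is stated as a correlation.
3. Prespecify sensitivity and specificity of B-FFR and CT-FFR at 0.80 or below, against I-FFR at 0.80 or below, with exact 95% CIs. Study Design/ Procedures says "The invasive FFR will be done on the culprit lesion(s) for clinical purposes", so if more than one lesion per patient is analysed, use intervals that allow for clustering within patients.
4. Keep Pearson r, AUC and absolute percent error against I-FFR.

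The cost is a few sentences of wording and a few lines of analysis on data already collected, with no extra patients or tests. The intervals will be wide at N = 52. For example, sensitivity 18/23 has an exact 95% CI of 56% to 93%, and specificity 23/29 has 60% to 92%. With error SD 0.12 the limits of agreement are bias ± 1.96 × 0.12 = ± 0.235. Each limit has a CI half-width of 2.008 × 0.12 × √(1/52 + 1.96²/102) = 0.057. The report should state this imprecision.

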For each patient a 3D printed phantom will be made and tested. Segmentation will be performed in Vitrea, vascular mesh sculpting in Autodesk Meshmixer, and 3D printed in a Stratasys Eden 260V printer (Stratasys, Eden Prairie, MN) printer. Figure 1 shows the model development process. Each 3D printed patient-specific model will be connected to a flow loop using the CardioFlow 5000 MR programmable physiological pulsatile flow pump (Shelley Medical Imaging Technologies, Toronto, Ontario, Canada) and a Benchtop FFR will be obtained. This pump introduced a physiologic human cardiac waveform and provided also an ECG signal triggered at points within the cardiac waveform. The viscosity of blood (approximately 3.7 cP) will be mimicked using a glycerol water solution of 40% water and 60% glycerol and measured using a viscometer. Figure 2 shows the benchtop flow system.

Reconstructed CCTA images were imported into Vitrea segmentation software (Vital Images, Minnetonka, MN) using the research-based CT-FFR algorithm [26-28]. The software analyzes four data volumes acquired a 70-99% of the R-R interval and computes the FFR based on the changes in vessel diameter and computational fluid dynamics.

Figure 1: Model development process. (a) The cardiac mesh was exported as a stereolithographic file from Vitrea into Autodesk Meshmixer. (b) The daughter branches off of the 3 main coronary arteries were cut off from the mesh. (c) The aortic root was extended at both the outlet and inlet with 30 mm diameter for later connections (red arrows). Cylindrical meshes were appended (red circles) to the aortic root and each of the coronary arteries for later pressure sensor connections. (d) Each coronary artery was extended. (e) A plane cut was administered at the vessel outlets for parallel ends. (f) A 2 mm wall was generated while preserving the geometry of the arteries. (g) A support structure is positioned around the model and the Boolean union operation is administered.

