Figure 2: Benchtop flow system. (a) A 3D printed patient-specific coronary model is connected to a flow loop using the Cardio Flow 5000 MR programmable physiological pulsatile flow pump (Shelley Medical Imaging Technologies, Toronto, Ontario, Canada). The flow loop consisted of two compliance chambers, at the aortic inlet (D1) and distal to the coronary arteries (D2) to control pressure oscillation and distal resistance. Aortic base pressure and distal flow rate were controlled by adjustable mechanical clamps (R1 and R2 respectively), and flow rate was recorded using an ultrasonic flow sensor (S). Flow direction is indicated by blue arrows. (b) Detailed side view of the 3D printed coronary model with pressure sensors connected to the aorta and the LAD. (c) Coronary waveform within the coronary flow pump software to determine the flow rate (mL/s) as a function of time in a single cardiac cycle. (d) 52 patient-specific 3D printed coronary models assembled and ready to go through flow testing.

Inclusion Criteria

- Scheduled for clinically mandated elective invasive coronary angiography (ICA) or clinically mandated CTA
- \circ >18 yrs of age

Exclusion Criteria

- Less than 30 years of age
- Atrial fibrillation
- Renal insufficiency (estimated glomerular filtration rate (GFR) <60 ml/min/1.73 m2)
- Active Bronchospasm prohibiting the use of beta blockers
- Morbid obesity (body mass index 40 kg/m2)
- o Contraindications to iodinated contrast
- Emergencies requiring immediate intervention or patients unable to consent
- Patients not showing coronary calcium during Calcium Scoring procedures

Sample Size

To determine the numbers of phantoms needed for this study we treated 3D printing as a new diagnostic tool for which we needed to assess the accuracy of detecting significant FFR values. We used the sample size calculation proposed by Flahault et. al. [23].

$$n = \frac{\left(z_{\alpha/2}\sqrt{\hat{V}(\hat{A})}\right)^2}{L^2}$$

Since this is a technical feasibility study, we wanted to estimate the ROC area to within ± 0.6 ; thus, L=0.12 and the confidence level was set at 0.92 which corresponds to $z_{\alpha/2}=1.75$. For the variance function we used the formulation indicated by Obuchhowski et al. [24] who proposed an estimate of the variance function for the Receiver Operator Characteristic based on an exponential distribution.

$$\hat{V}(\hat{A}) = (0.0099 \times e^{a^2/2}) \times [(5a^2 + 8) + (5a^2 + 8)/R]$$

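### The ROC analysis reports B-FFR and CT-FFR separately, with no paired comparison and no stenosis benchmark, so the AUCs alone cannot show that either index ranks lesions better than lumen narrowing does.

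*Combined protocol and SAP*

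**What the plan says.** Statistical Analysis plans two kinds of result, each against I-FFR. One is agreement on the FFR scale and correlation: "The absolute error as a percentage with 95% confidence intervals and Pearson correlation values will be calculated". The other is discrimination: "A ROC curve will also be generated to determine the area under the curve (AUC) for B-FFR and CT-FFR when compared to I-FFR". The section names no third index, no minimum or null AUC, and no difference between AUCs. The cutoff is in Study Design/ Procedures: "A FFR cutoff value of less than or equal to 0.8 was used to determine hemodynamic significance".

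Both indices start from the CCTA. For the phantom, the caption of Figure 1 says: "The cardiac mesh was exported as a stereolithographic file from Vitrea into Autodesk Meshmixer". For CT-FFR, Study Design/ Procedures says that the software takes the reconstructed CCTA images and "computes the FFR based on the changes in vessel diameter and computational fluid dynamics".

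Stenosis enters at eligibility: "First requirement is that the patient has at least one lesion with >50% stenosis or 30-50% if clinically driven". The same section says: "Patients will be consented after CCTA".

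On purpose, Sample Size says that "we treated 3D printing as a new diagnostic tool for which we needed to assess the accuracy of detecting significant FFR values". The Objectives include an FFR-CT algorithm that predicts lesion severity better, and the Summary of Proposed Research makes clear that this means better than methods now on the market.

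**The concern.** The phantom is a physical copy of the CCTA lumen, and CT-FFR is computed from the same scan. Entry starts at 30% stenosis and no upper limit is stated, so the sample may span a range of narrowing. Any measure that follows narrowing will then rank lesions against I-FFR to some degree. A good AUC could reflect the flow measurement or computation, or only the fact that tighter lesions tend to have lower FFR. A stand-alone AUC does not separate the two explanations. The AUC of stenosis on the same lesions would help to do so, and it is not planned.

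The plan also makes no use of the pairing. Each patient contributes both B-FFR and CT-FFR, and two separately reported AUCs leave the reader to compare them without an interval for the difference.

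What is at stake is interpretation. An AUC near 0.80 could be taken as evidence that phantom flow or CT-FFR adds to anatomic stenosis, when the ROC analysis contains nothing that bears on that.

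**Working it through.** **Inputs from the documents** (Sample Size): AUC 0.80 with a = 1.19; R = 1.2; L = 0.12; z = 1.75; about 23 patients with FFR ≤ 0.80; total about 52, which leaves 52 − 23 = 29 without.

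**Assumed, because the documents give no value:** the correlation of stenosis with I-FFR (0.3 to 0.7 in size), and the correlation between two AUC estimates on the same patients (0.3 to 0.7).

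**Step 1. The plan's own figure.** n = z²V/L² and N = n(1 + R). The variance formula as it reads in the text (positive exponent, 5a² + 8 in both terms) gives V = 0.556, n = 118 and N = 260. With a negative exponent and a² + 8 in the second term:

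- V = 0.0099 × e^(−1.4161/2) × [(5 × 1.4161 + 8) + (1.4161 + 8)/1.2] = 0.0099 × 0.4926 × (15.08 + 7.85) = 0.1118
- n = 1.75² × 0.1118 / 0.12² = 23.8
- N = 23.8 × 2.2 = 52.3

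This reproduces 52, so V = 0.1118 is used below. A sign may have been lost when the PDF was read.

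**Step 2. What an AUC of 0.80 can exclude.** Hanley-McNeil variance with 23 positives and 29 negatives:

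- Q₁ = 0.80/1.20 = 0.667; Q₂ = 2 × 0.64/1.80 = 0.711
- Var = [0.80 × 0.20 + 22 × (0.667 − 0.64) + 28 × (0.711 − 0.64)] / (23 × 29) = 0.00410; SE = 0.064
- 95% interval: 0.80 ± 1.96 × 0.064 = 0.67 to 0.93

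This excludes 0.5.

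**Step 3. What stenosis alone might give.** Take stenosis and I-FFR as bivariate normal, with a share 1/(1 + 1.2) = 0.45 of patients positive.

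| Assumed correlation (size) | AUC of stenosis alone |
|---|---|
| 0.3 | 0.64 |
| 0.4 | 0.68 |
| 0.5 | 0.73 |
| 0.6 | 0.78 |
| 0.7 | 0.83 |

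The interval in Step 2 covers the values for correlations of 0.4 and above; the value at 0.3 falls just below it. Reading one interval against a fixed number is only a rough guide, because stenosis would be measured on the same patients and have its own sampling error. That is why the paired difference is needed.

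**Step 4. Precision of a paired difference at N = 52.** The number of positives is 52/2.2 = 23.64, so the SE of one AUC is √(0.1118/23.64) = 0.0688. With equal SEs, the SE of the difference is 0.0688 × √(2(1 − r)), where r is the correlation between the two AUC estimates.

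| r | SE of difference | 95% half-width |
|---|---|---|
| 0.3 | 0.081 | 0.16 |
| 0.5 | 0.069 | 0.13 |
| 0.7 | 0.053 | 0.10 |

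Treating the two AUCs as independent (r = 0) would give 0.19. The plan proposes no such comparison; the figure shows only what is lost by ignoring the pairing.

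**The case against.** The strongest objection is that gain over stenosis is not a question this study asks. The Hypotheses concern correlation of phantom flow with CT-FFR, and Sample Size calls the work a technical feasibility study. For a validation phantom, faithful copying of the lumen is a virtue. This stands: it makes the stenosis contrast exploratory. The paired B-FFR minus CT-FFR difference is closer to the study's own question.

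A reader might infer that the study as a whole cannot tell a working flow measurement from a copy of the stenosis. The documents do not support that. The planned percentage error against I-FFR is on the FFR scale, where a measure that merely ranks narrowing has no direct route to small error. The limit applies to the ROC analysis. Pearson correlation does not fill the gap, because it too rises with the spread of severity and is not compared with stenosis.

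A reader might also infer that beating stenosis would establish the better predictability that the Summary of Proposed Research expects. It would not, because the comparator there is marketed FFR-CT methods.

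Nor do the documents say that a numeric CCTA stenosis is already on file for each lesion. They give a category for at least one lesion, do not name the modality, and do not say that the qualifying lesion is the one given I-FFR. Consent after CCTA makes a CCTA reading likely, but that is an inference. The actual mix of mild and severe lesions is also undocumented.

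Finally, the yield is limited. With an index AUC of 0.80, an assumed stenosis AUC of 0.65 to 0.75 and r from 0.3 to 0.7, power to detect the difference (two-sided 5%, Hanley-McNeil SEs) runs from 9% to 76%. This supports reporting estimates with intervals and not a test.

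**Conclusion.** The point holds as a cheap improvement to the ROC analysis. Without a paired difference or a geometry-only benchmark, an AUC near 0.80 says that an index discriminates better than chance. It does not say that the index ranks lesions better than lumen narrowing, or that one index ranks them better than the other. The AUCs themselves are not invalidated, and 0.80 is only a planning value for precision, not a success threshold.

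The size rests on assumption. A stenosis AUC of 0.64 to 0.83 follows from an assumed correlation of 0.3 to 0.7 and bivariate normality. It exceeds 0.80 only near the top of that range, and nothing in the documents rules out the lower values. The half-widths rest on assumed AUC correlations and on the variance form that reproduces 52.

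**What to change.** Add to Statistical Analysis:

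- The difference in AUC, B-FFR minus CT-FFR, for I-FFR ≤ 0.80 will be reported with a paired 95% DeLong interval.
- Percent diameter stenosis of the lesion given I-FFR will be recorded as a number from the existing CCTA, by a stated measurement rule.
- The AUC of that stenosis, and the paired differences B-FFR minus stenosis and CT-FFR minus stenosis, will be reported with 95% DeLong intervals as exploratory estimates.
- Any statement that either index adds to anatomic stenosis will rest on those differences. They will not be used to claim superiority over marketed FFR-CT products.
- The report will note that selecting patients on stenosis restricts its range and may lower its AUC in this sample.

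The cost is a few lines of text and one stenosis measurement per lesion on images already acquired, which may mean a new reading. No extra patient or procedure is needed. The downside is imprecise differences, and a result that may well be inconclusive.
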